#### *D.7.1.1.2 AEE, Adipocytokines and Diabetes*

We will have measures of fasting glucose and insulin, adiponectin, ghrelin and leptin on this unique sample of 5 populations of African origin. The following additional variables will be collected: age, gender, place of birth, prior medical history, occupation, education, height, weight, activity by questionnaire, pregnancy history, and season of exam.

In the analysis phase we will first compare the descriptive characteristics in each population (e.g., mean adipocytokine/hormone values and prevalence of hyperglycemia). We will explore the univariate correlation structure for the continuous variables listed above. We will then construct multivariable regression models to assess the potential independent role of AEE as a predictor of risk factor status independent of body composition. Risk factor status will be examined as continuous and categorical outcomes. For instance, how is insulin level affected by AEE after accounting for body composition?

An important focus of these analyses will be looking for potential heterogeneity of risk relationships across sites. Three main aspects are of interest, namely whether the AEE-risk factor (e.g. insulin level) relationship is present, or of the same magnitude, in each sample and whether there exists co-variation with the mean level of AEE; testing for interaction will be undertaken where appropriate. Precisely,

*Relative effect of AEE on risk factor:* We will examine the magnitude of the association using 1) regression coefficients; 2) standardized regression coefficients. This approach allows within and between site comparisons. It is recognized that cross-site comparisons could be problematic when using standardized regression coefficients since the standard deviation of the variables involved may differ across sites. In this case, standardized regression coefficients will be obtained using pooled estimates of the mean and standard deviation.

*Co-variation of the association with mean level of AEE:* Multilevel models will be applied, in which the site specific variable, mean AEE, will be used to estimate the effect of the average AEE on the regression coefficient.

*Interactions between AEE and site:* Multiplicative interaction terms will be included in regression models to assess how much site modifies the association between AEE and the risk factor. We are fully aware of the lack of statistical power to test this type of hypotheses and thus results will be exploratory in nature. Thus, one might anticipate that anthropometric and AEE measures are stronger in low risk population samples than in the US. In addition, we will test whether the slope of the exposure-outcome relationships are influenced by the mean BMI of the population using multilevel regression models.

Questionnaire data on AEE will be summarized using methods previously developed [188]. Mean activity levels and prevalence of inactivity will be assessed in relation to objective measures of EE and the relevant outcome variables. As a sub-analysis we will describe types of activities reported to assess overall population patterns.

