## **A. SPECIFIC AIMS**

Populations all over the world are experiencing rapid increases in the prevalence of obesity and diabetes [1-5]. To date, the public health response to the emerging obesity epidemic has been almost totally ineffective. As a first line of response, professional bodies and government organizations have issued prevention guidelines, all of which include recommendations on levels of activity energy expenditure (AEE) [6-10]. However, even if fully implemented, it is not clear that the current recommendations on AEE would impact the trend in age-related weight gain. *In fact, there is virtually no direct evidence that can be brought to bear on the question of whether the obesity epidemic has resulted primarily or even partially from society-wide declines in habitual physical activity (PA).*

To date, epidemiologic research on AEE has relied on very crude measurement tools—primarily questionnaires. These self-reported data capture only a small fraction of the total variance in activity and are potentially confounded when they focus on leisure-time PA. By contrast, direct measurement with doubly labeled water (DLW) provides a precise, unbiased estimate of all forms of non-resting energy expenditure. DLW has also been used to validate the new generation of accelerometers which are efficient measurement tools for larger studies.

In this application we request support to apply these objective measurement tools to examine the “ecology of AEE”. The study will take place in 5 countries, spanning the range of the activity-obesity spectrum, and combine both within-population person-level and between-population ecological analyses. First, we will examine whether an individual’s amount or pattern of AEE is related to adiposity in a diverse sample of 2,500 (i.e., 500 subjects/site x 5 sites). Second, we will test the ecological hypothesis that a decline in levels of AEE is an important cause of the rapid increases in obesity that are currently taking place in many societies. As an exploratory aim we will examine the role of selected adipocytokines and the appetite hormone ghrelin.

*Accordingly, we propose to test the following Hypotheses:*

- 1) AEE is negatively related to percent body fat in the 5 study populations at baseline, independent of dietary intake.
- 2) AEE is negatively related to change in body weight during follow-up, independent of dietary intake.

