**Table 5. Proposed Study Measures**

	Baseline (N)	12-Mo Follow-Up (N)	24-Mo Follow-Up (N)	Use of Data
Physical Activity				
Accelerometer	2500		2500	Exposure
DLW	375			Concordance, exposure
Questionnaire	2500			Exposures
Body Composition				
BIA	2500		2500	Outcome: baseline & change
Isotope Dilution	500		500	Calibrate BIA change data
Dietary Intake	2500			Covariate
Anthropometrics	2500	2500	2500	Outcome: baseline & change
Blood pressure	2500			Outcome
Adipocytokines/Hormones	2500			Outcome

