### **D.7.1 Statistical Analysis**

In the initial stage of the analysis, a complete set of descriptive tables will be produced by gender within site. The distributional properties of each variable will be examined and appropriate re-scaling undertaken, if necessary. All outliers (i.e.  $> 3$  SD's) will be identified and either verified as correct or set to missing. When possible, internal validity will be assessed by the use of bivariate scatter plots of variables known to be correlated (e.g., resting EE vs. BMI or weight vs. BP). These plots provide a useful search procedure for unanticipated outliers and/or non-linear relationships.

As in any other longitudinal study, some measurements may be unavailable in a subset of the study participants. A brief description of methods used to handle non-ignorable missing data are presented at the end of this section (cf. D.7.4)

*We describe below the analytic procedures and the power calculation, in relation to the following 4 primary hypotheses as stated in the Aims:*

- 1) AEE is negatively related to % body fat at baseline, independent of dietary intake.
- 2) AEE is negatively related to change in body weight during follow-up, independent of dietary intake.
- 3) Mean levels of AEE are negatively related to mean levels of obesity/relative weight among the populations.
- 4) Adipocytokines and hormones influence weight regulation and insulin sensitivity and interact with AEE.

[figure not shown]

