Where  $T_{i1} = 0$ ,  $T_{i2}=12$ , and  $T_{i3}=24$  correspond to the three times at which weight will be measured for the  $i$ -th subject;  $X_i$ , and  $Z_i$  are potential confounders; and  $\Omega$  and  $\Psi$  are model parameters associated to the confounders. Confounders will include demographic variables and EI variables (e.g. total intake, percent calories from fat, etc). This approach corresponds to a multivariate nutrient density method suggested in the literature [73]. The effect of type of food most frequently consumed (e.g. vegetables, industrially processed foods, etc) will be accounted for by including dummy variables in our multivariate regression models. Note that the parameter  $\beta_{1i}$ , in the Level-1 equation, represents the weight change of the  $i$ -th subject. Thus, the Level-2 equation for this parameter models the dependence of weight change on AEE after adjusting for other covariates. A similar interpretation for the intercept parameter,  $\beta_{0i}$ , holds. In both instances site-specific factors could be included.

The multilevel approach can be extended to accommodate time-varying covariates, which we will apply to investigate the effect of changing AEE on weight change. In addition, the effect of AEE in the  $i$ -th subject ( $\Delta AEE_i$ ) on weight change will be assessed by replacing  $AEE_i$  in the Level 2 step of the multi-level analysis above by ( $\Delta AEE_i$ ).

Finally, one additional co-variate capturing exposure information will be created which will define the pattern of AEE. After examining the within-person distribution over the monitored days (eg, within-person SD) we will use both continuous and categorical transformations to characterize "consistent vs variable" patterns. Our pilot data suggest substantially more consistent patterns in Nigeria vs. the US and this may impact on the AEE-weight relationship.

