## D.7.2 Power Analysis

A statistical justification for the selected sample size is provided for each aim of the study according to the suggested analytical plan. Sample size estimation for each of these hypotheses will be obtained, and the maximum number required to test them with sufficient power (80% or higher) will be selected.

- 1) PA is negatively related to percent body fat and CV risk factors in the study populations at baseline.

It has been previously estimated (cf. Preliminary Studies) that the correlation between PA, measured with DLW, and body composition is between -0.6 and -0.5. A correlation of -0.33 or smaller (larger in absolute value) will be detectable with 83% power and maximum probability of type I error alpha = 5% using a one-sided Fisher's Z test and 75 subjects per site [194].

- 2) PA is negatively related to change in body fat composition.

- a) *Physical Activity Measured by Accelerometer:*

PA, measured by the accelerometer, is associated with changes in body composition. For design purposes we will use the approach described above in the analysis section (see D.7.1.2. method 3). That is, two AEE groups will be formed by using the median AEE as the cut point. A method developed by Frison and Pocock [195] will be applied to compare mean changes between groups in a longitudinal analysis, adjusting for baseline values. In this method the following assumptions are made: the correlation between any 2 weight determinations is ~ 0.60 and the minimum acceptable difference between the means is 0.25 standard deviations (i.e., effect size equals 0.25) [186]. There will be one baseline measure of weight and two follow-up measurements. An analysis of covariance approach will be used to adjust for baseline values. Thus, to detect the pre-specified minimum difference with 90% statistical power we will need to accrue 460 subjects per AEE group (230 in the Low and 230 in the High group). We will accrue a total of 500 individuals per site in anticipation of a conservative total attrition rate of ~ 20%.

- b) *Physical Activity Measured by Doubly Labeled Water:*

The correlation between AEE and change in body composition is anticipated to be weaker (i.e., smaller in absolute value) than that observed between AEE and body composition at baseline. Data from previous studies (cf. Section C: Preliminary Studies) suggest that the association between AEE and body composition remains constant across studies.

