Although the study is not powered to test for differences in the association across sites (i.e., effect modification), we will undertake this task to ensure that large differences among the correlation coefficients do not exist. In addition, sites in which the correlation coefficient is deemed to be similar will be combined, and then comparisons of the correlations will be performed. For the sake of illustration, assume that 2 sites ( $n = 150$  individuals) are compared to other 2 sites ( $n = 150$  individuals). Thus, a two-sample, one-sided test of the correlations, assuming -0.4 versus -0.65, will yield over 91% power, whereas the power will be over 80% for comparison of -0.45 and -0.65, and between -0.35 and -0.6 the power is greater than 85%. Combining the data samples from all 5 sites and assuming constant

association will demonstrate a correlation between AEE and change in body composition of -0.15 or smaller (larger in absolute value) with over 83% power.

3) Mean levels of AEE are negatively related to mean levels of obesity/relative weight among the populations.

As previously demonstrated, sample sizes within sites will allow us to rule out correlations larger than 0.33 (absolute value), even when AEE is determined by DLW. Furthermore, we have estimated (cf. Preliminary Studies) that the within-site correlation between AEE and body composition of individual data could be as large as 0.6. We anticipate that the correlation between mean AEE levels and mean body composition will exceed 0.85. This estimate is justified in the following manner. A Fisher's Z-transformation 5%-significance test will have over 55% power to detect this correlation with 5 values corresponding to the 5 sites of the study. However, after dividing our samples by gender there will be 10 observations (2 X 5 countries), resulting in over 95% statistical power. Assuming an effective sample size of 7, to account for within-country correlations, the statistical power is 80%. Note that additional power will be gained when weighted linear regression methods are applied to estimate the correlation (slope) between AEE and body composition using meta-regression. Given the strong a prior hypothesis we can also compare mean AEE in the groups with the highest and lowest rates of obesity to test the ecological association.

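### Hypothesis 4 on hormones is called primary in one place and exploratory in another, has no power statement, and is not tested by the regressions as specified

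*Combined protocol and SAP*

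**What the plan says.** **Status.** D.7.1 opens its list with "We describe below the analytic procedures and the power calculation, in relation to the following 4 primary hypotheses as stated in the Aims". The fourth item is "Adipocytokines and hormones influence weight regulation and insulin sensitivity and interact with AEE". Section A says of the same work: "As an exploratory aim we will examine the role of selected adipocytokines and the appetite hormone ghrelin".

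**Power.** D.7.2 begins: "A statistical justification for the selected sample size is provided for each aim of the study according to the suggested analytical plan". Its numbered items end with the third, "Mean levels of AEE are negatively related to mean levels of obesity/relative weight among the populations". D.7.3 on data management follows.

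**Hormone analysis.** D.7.1.1.2 plans descriptive comparisons by site, then univariate correlations among the listed continuous variables (which include insulin, glucose, leptin, adiponectin, ghrelin and weight), then multivariable models to "assess the potential independent role of AEE as a predictor of risk factor status independent of body composition". The worked example asks how AEE affects insulin once body composition is accounted for. In Table 5 the row "Adipocytokines/Hormones" is measured at baseline in 2,500 people and its use is given as an outcome.

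**Weight-change analysis.** All four steps of D.7.1.2 use AEE as the exposure. For the mixed model the text says: "Confounders will include demographic variables and EI variables". No hormone is named.

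**The concern.** Hypothesis 4 has three parts: hormones affect weight regulation, hormones affect insulin sensitivity, and hormones interact with AEE. In each part a hormone is the explanatory variable or the modifier. The specified regressions put AEE on the explanatory side and the risk factor, hormones included, on the outcome side. An AEE coefficient in a model for leptin or insulin says nothing about whether a hormone predicts later weight change.

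Without a named model, outcome, hormone list or multiplicity rule, any claim on Hypothesis 4 would rest on analyses chosen after the data were seen. With three hormones, two outcomes, main effects and interactions, there is ample room for selective emphasis. The primary label makes this worse, because a reader would take the result as pre-specified and powered. The conflict between Section A and D.7.1 leaves the status of the result open.

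**Working it through.** **Step 1: match each part of the hypothesis to the plan.**

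| Part of Hypothesis 4 | What is specified | Gap |
|---|---|---|
| Hormone and weight regulation | Unadjusted baseline correlation with weight (D.7.1.1.2); weight-slope model with AEE, demographic and intake covariates (D.7.1.2) | No adjusted or longitudinal hormone estimate |
| Hormone and insulin sensitivity | Unadjusted baseline correlation with insulin; adjusted model with AEE as predictor | No adjusted model with a hormone as predictor |
| Hormone by AEE | AEE by site; site mean AEE acting on the coefficient; population mean BMI acting on the slope (all D.7.1.1.2) | No AEE-by-hormone term |
| Power | Items 1 to 3 of D.7.2 | No item 4 |

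D.7.1.1.2 also has a general remark on testing for interaction where appropriate. It sits in a passage on heterogeneity across sites, and the detail that follows concerns AEE and site characteristics, not hormones.

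The unadjusted correlations cannot fill the gap. B.8 itself says that leptin accurately reflects fat mass, so a raw leptin-weight or leptin-insulin correlation may be adiposity alone.

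**Step 2: the plan's own figure.** There is none for Hypothesis 4. The power figures in D.7.2 concern AEE or physical activity against body composition, its change, or population means. None involves a hormone.

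**Step 3: what the planned sample could detect.** Inputs from the documents: 500 per site and 2,500 in total at baseline; at most 20% attrition by 24 months, so 400 per site and 5 × 400 = 2,000 in total (D.1.1). Assumptions, because the documents give none for this hypothesis: 80% power, two-sided tests, Fisher's Z approximation.

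Minimum detectable partial correlation = tanh[(z for alpha + z for power) / √(n − 3)], with z for power = 0.8416.

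- One test at 5%: 1.9600 + 0.8416 = 2.8016
- Alpha/3 (three hormones): 2.3940 + 0.8416 = 3.2356
- Alpha/6 (three hormones, main effect and interaction): 2.6383 + 0.8416 = 3.4799

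| Alpha | Weight change, pooled N = 2,000 (√1997 = 44.69) | Weight change, per site n = 400 (√397 = 19.92) | Baseline insulin, N = 2,500 | Baseline insulin, n = 500 |
|---|---|---|---|---|
| 5%, uncorrected | 0.063 | 0.140 | 0.056 | 0.125 |
| Alpha/3 | 0.072 | 0.161 | 0.065 | 0.144 |
| Alpha/6 | 0.078 | 0.173 | 0.070 | 0.155 |

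**Step 4: range over assumed effects.** Power before any multiplicity correction, two-sided 5%:

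| Assumed partial correlation | N = 2,000 | n = 400 |
|---|---|---|
| 0.02 | 14% | 6% |
| 0.03 | 27% | 9% |
| 0.05 | 61% | 17% |
| 0.10 | 99% | 52% |

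A pooled test is feasible for effects of about 0.07 to 0.08 or more. Single-site tests are weak below about 0.16 to 0.17.

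**The case against.** The strongest reply has four parts.

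- **An exploratory aim needs no formal power calculation, and Section A calls this one exploratory.** This largely stands. Once the label is settled, the missing power matters much less. What remains is the contradiction with D.7.1 and the statement in D.7.2 that each aim is covered.
- **The plan is not silent on hormones.** Univariate correlations including hormones, insulin and weight are planned, and Specific Aim 4 speaks of inter-relations between AEE and the hormones. This also stands, so it would be wrong to say that no planned estimate bears on the hypothesis. But those estimates are unadjusted and cross-sectional.
- **To interact with AEE may mean to be related to it, not a product term.** The wording allows this, and D.7.1.1.2 would then address that part. It would still leave the weight and insulin parts without an adjusted model.
- **No text says that an AEE-leptin association would be taken as proof that hormones drive weight.** Correct. B.8 recognises the link between leptin and fat mass, and D.7.1.1.2 adjusts for body composition. The risk is an unspecified test; no misreading is announced in the plan.

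A reader might also infer that AEE by site is the only effect modification planned. It is not: site mean AEE and population mean BMI are also allowed to modify slopes. None of these involves a hormone.

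**Conclusion.** The point holds as a gap in specification and a conflict of labels. Hypothesis 4 is primary in D.7.1 and exploratory in Section A. D.7.2 gives it no power. The stated regressions run in the opposite direction to the hypothesis, so following them yields no adjusted or longitudinal hormone estimate and no AEE-by-hormone estimate.

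A reader might go further and infer that the study cannot answer Hypothesis 4. The documents do not support that. Baseline hormones, insulin and AEE are planned in 2,500 people, with weight at 0, 12 and 24 months, which is the time order a hormone-to-weight-change test needs. Nor do the figures show that the sample is too small: pooled detectable partial correlations are about 0.072 (alpha/3) to 0.078 (alpha/6), and 0.161 to 0.173 per site. Whether that suffices cannot be judged, because no expected effect is stated.

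These figures assume 20% attrition, 80% power, two-sided tests and a Fisher's Z approximation. Hypotheses 1 to 3 are not affected. The change should be made, but it concerns a question that Section A already treats as exploratory.

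**What to change.** 1. In D.7.1, label Hypothesis 4 exploratory, to match Section A. Amend the opening of D.7.2, and the promise in D.7.1, so that they no longer claim a sample-size justification for every aim.
2. In D.7.1.2, add the baseline hormone H (leptin, adiponectin and ghrelin in turn, transformed if needed) and its product with AEE to the Level-2 slope equation: β₁ᵢ = α₀ + α₁AEEᵢ + α₂Hᵢ + α₃(AEEᵢ × Hᵢ) + ΨZᵢ + ξ₁ᵢ, with site and baseline body composition in Z. For leptin, report the model with and without fat mass: the two are closely related, and adjustment changes what the coefficient means.
3. In D.7.1.1.2, add a matching baseline model with fasting insulin as outcome and hormone and AEE × hormone as predictors, with the same covariates.
4. State how many tests the multiplicity correction covers (hormones, main effect and interaction, outcomes), and give detectable partial correlations on that basis. For weight change these are 0.072 pooled and 0.161 per site at alpha/3, or 0.078 and 0.173 at alpha/6. If both outcomes share one family, recompute.

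The cost is a few model terms and some paragraphs of text, with no new participants, visits or assays. Hypothesis 4 loses its primary label.

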#### *D.7.1.2 AEE and Weight Change*

The study design contemplates 3 weight determinations over time: one at baseline, a second after 12 months, and a final assessment 2 years after entering the study. To better understand the associations between AEE and body composition, the analysis plan will be carried out in incremental steps corresponding to the degree of sophistication of the statistical methods used.

- 1) Descriptive: Weight change is computed for each subject as the subject's last weight minus baseline weight. The correlation between weight change and AEE will be computed.
- 2) Regression of weight change (as computed above) on AEE will be performed, adjusting for potential confounders of the association.
- 3) AEE will be dichotomized at the median value, resulting in high and low AEE groups. Weight change will be estimated for each individual as the slope of the regression of weight on time (0, 12, and 24 months). Average weight change across AEE groups will be compared. That is, individual regression lines of weight on time will be obtained for each individual, and the average regression among "Low PA" will be compared to the average regression among "High PA" subjects.
- 4) Multilevel analysis (i.e., mixed effect models), which generalizes the previous methods, will be used in our final analysis. This approach will allow for the use of all the available information (i.e., there will be no need to categorize AEE values), thus improving the statistical power [189]. Furthermore, this method allows one to account for the within-subject correlation of the weight determinations and to account (adjust for) subject-specific covariates that may confound the associations. In addition, the dependence of weight change on AEE values can be specifically modeled by the use of random coefficients. Specifically,

$$\text{Level 1: } W_{ij} = \beta_{0i} + \beta_{1i} T_{ij} + \varepsilon_{ij}$$

$$\text{Level 2: } \beta_{0i} = \gamma_0 + \gamma_1 AEE_i + \Omega X_i + \xi_{0i}$$

$$\beta_{1i} = \alpha_0 + \alpha_1 AEE_i + \Psi Z_i + \xi_{1i}$$

$$\varepsilon_{ij} \approx N(0, \sigma^2); \xi_{0i} \approx N(0, \delta_0^2); \xi_{1i} \approx N(0, \delta_1^2); \text{corr}(\xi_{0i}, \xi_{1i}) = \delta_{01}$$

$$\text{corr}(\varepsilon_{ij}, \xi_{0i}) = \text{corr}(\varepsilon_{ij}, \xi_{1i}) = 0$$

$$i = 1, \dots, n; \quad j = 0, 1, 3$$

Where  $T_{i1} = 0$ ,  $T_{i2}=12$ , and  $T_{i3}=24$  correspond to the three times at which weight will be measured for the  $i$ -th subject;  $X_i$ , and  $Z_i$  are potential confounders; and  $\Omega$  and  $\Psi$  are model parameters associated to the confounders. Confounders will include demographic variables and EI variables (e.g. total intake, percent calories from fat, etc). This approach corresponds to a multivariate nutrient density method suggested in the literature [73]. The effect of type of food most frequently consumed (e.g. vegetables, industrially processed foods, etc) will be accounted for by including dummy variables in our multivariate regression models. Note that the parameter  $\beta_{1i}$ , in the Level-1 equation, represents the weight change of the  $i$ -th subject. Thus, the Level-2 equation for this parameter models the dependence of weight change on AEE after adjusting for other covariates. A similar interpretation for the intercept parameter,  $\beta_{0i}$ , holds. In both instances site-specific factors could be included.

The multilevel approach can be extended to accommodate time-varying covariates, which we will apply to investigate the effect of changing AEE on weight change. In addition, the effect of AEE in the  $i$ -th subject ( $\Delta AEE_i$ ) on weight change will be assessed by replacing  $AEE_i$  in the Level 2 step of the multi-level analysis above by ( $\Delta AEE_i$ ).

Finally, one additional co-variate capturing exposure information will be created which will define the pattern of AEE. After examining the within-person distribution over the monitored days (eg, within-person SD) we will use both continuous and categorical transformations to characterize "consistent vs variable" patterns. Our pilot data suggest substantially more consistent patterns in Nigeria vs. the US and this may impact on the AEE-weight relationship.

